the best of our knowledge, no such comparisons have yet been made in a cohort of morbidly obese (BMI \geq 40) pregnant women manifesting severe hypertension.

The conical Ultracheck Curve (reusable or single use) BP cuff (Statcorp Medical, Jacksonville, Florida, U.S.A.) is advertised (Sharn Anesthesia Inc., Tampa, Florida, U.S.A.) as: "A Breakthrough Solution for Accurate Bariatric Blood Pressure Readings. We intend to compare IBP readings obtained from morbidly obese, severely hypertensive (SBP > 160 mm Hg) parturients with NIBP consecutively measured with new innovative conical Ultracheck Curve BP cuffs and large standard upper arm rectangular cylindrical as well as radial BP cuffs.

Methods: Twenty-five morbidly obese (BMI \geq 40 kg/m²) severely hypertensive (SBP > 160 mm Hg) parturients with clinically indicated radial artery lines already in situ or who agree to placement of an arterial line after a thorough explanation of limited complications related to arterial line insertion will be recruited to the study. Both IRB approval and the patients' written informed consent for the study will be obtained. The following measurements (left and right arm) will be made and recorded with the patient lying in a 15° left lateral tilt position, arms by their side and forearms pronated:

- 1) Proximal upper arm circumference just below the axilla.
- 2) Distal upper arm circumference 0.5 cm above antecubital fossa.
- 3) Upper arm length axilla to the antecubital fossa.
- 4) Blood pressure cuff size

For comparative purposes BP will be measured and documented sequentially and in random order (computer generated random numbers table). NIBPs will be recorded using either an upper arm large adult [American Heart Association (AHA): 16-36 cm.] cylindrical BP cuff, a radial cuff, or an UltraCheck Curve bariatric BP cuff. The BP cuffs will be linked to an Oscillometric BP recording device (Philips M1574A). There will be an initial set of readings on admission, and subsequent sets of readings before a medication administration on the Vanderbilt Management Guideline for Acute Hypertension Algorithm. A set of readings will also be attained at decision for ICU transfer or cesarean section. SBP, MAP and DAP will be recorded from each cuff site (3 cuffs total) and then repeated after swapping the cuffs over to the opposite arm . Direct invasive arterial pressure readings will be charted simultaneously for comparative purposes.

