The primary outcome of this investigation will be to compare the agreement of NIBP and SBP measurements relative to IBP SBP recordings. Secondary outcomes will be: To compare the agreement of MAP and DAP NIBP recordings with IBP levels; to compare agreement of the SBP, MAP and DAP NIBP measurements obtained with cylindrical upper arm and radial BP cuffs with those recorded using conical BP cuffs.

Agreement between devices (NIBP vs IBP and NIBP cylindrical (upper and radial) versus conical BP cuffs) will be determined. The relationship between upper arm circumference minus distal arm circumference and upper arm cylindrical pressure and intra-arterial SBP difference

will be defined as well. The same relationship between upper arm minus distal arm circumference and conical cuff and intra-arterial SBP recordings differences will also be assessed.

Main Inclusion Criteria:

Written, signed and dated informed consent

 \geq 18 years of age

Morbidly obese (BMI \geq 40 kg/m²) severely hypertensive (SBP > 160 mm Hg) parturients with clinically indicated radial artery lines already in situ or who agree to placement of an arterial line after a thorough explanation of limited complications related to arterial line insertion will be recruited to the study

Gestational age greater than or equal to 24 weeks Parturients admitted for induction of labor

Exclusion Criteria:

Parturients admitted in labor

Statistical Plan:

Bland-Altman plots will be used to look at agreement of NIBP (SBP, MAP and DAP) and IBP. Regression analyses will examine the relationship between upper and lower forearm circumference measurements and difference between NIBP (SBP, MAP and DAP) cylindrical and radial cuffs versus conical (obesity) BP cuffs.

Based on the 2012 report from South Africa¹⁷ we estimate that 25 patients will initially need to be investigated. A difference of 10 mm Hg (SBP, MAP and DAP) will be considered clinically significant.

References:

- 3. Bramham K1, Parnell B, Nelson-Piercy C, Seed PT, Poston L, Chappell LC. Chronic hypertension and pregnancy outcomes: systematic review and meta-analysis BMJ. 2014 Apr 15;348:g2301. doi: 10.1136/bmj.g2301.

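### The plan does not make the arterial reference independent of the cuff result: it sets no data source, no averaging window and no masking

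*Combined protocol and SAP*

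**What the plan says.** All of this is in the Methods section of the combined protocol and SAP.

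- **Cuffs.** Three are compared: an upper arm "cylindrical BP cuff, a radial cuff, or an UltraCheck Curve bariatric BP cuff". They differ by shape or by site.
- **Cuff value.** It comes from an automated device: "The BP cuffs will be linked to an Oscillometric BP recording device (Philips M1574A").
- **Order.** "BP will be measured and documented sequentially and in random order (computer generated random numbers table").
- **Repeat.** "SBP, MAP and DAP will be recorded from each cuff site (3 cuffs total) and then repeated after swapping the cuffs over to the opposite" …
- **Arterial reference.** One sentence covers it: "Direct invasive arterial pressure readings will be charted simultaneously for comparative purposes".
- **Primary outcome.** It is to "compare the agreement of NIBP and SBP measurements relative to IBP SBP recordings".

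The Statistical Plan adds Bland-Altman plots and a margin ("A difference of 10 mm Hg (SBP, MAP and DAP) will be considered clinically significant"). It says nothing further about how the arterial value is obtained.

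**The concern.** The cuff gives one automatic number. The arterial pressure is continuous, so some rule must reduce it to one SBP, MAP and DAP per cuff reading. The plan gives no such rule, so any discretion lies in the reference. The operator knows which cuff is in use, and nothing says that whoever records the arterial value is unaware of the cuff result.

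Each cuff reading has its own arterial value, so discretion can act differently for different cuffs. Random order balances time and sequence effects, but it does not make the reference independent of the cuff.

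The arm swap adds a second gap. With one arterial line (an assumption), one of each cuff's two readings falls on the catheter arm. There the arterial trace is interrupted during inflation. A strictly simultaneous arterial value may not exist, and no substitute is defined.

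The arterial value enters every primary difference, the MAP and DAP agreement, and the two analyses relating arm-circumference difference to the cuff–arterial SBP difference. If it was charted with discretion, the analysis cannot repair it, and more patients do not shrink the error.

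**Working it through.** The plan gives no figure for reading error or masking, so there is none to reproduce. The calculation below only shows what size is possible.

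**Inputs from the documents**
- Cuff minus arterial SBP: mean −24, SD 17 mm Hg (oscillometric readings in the 23-patient preeclampsia study described in Background and Significance).
- Margin 10 mm Hg and 25 patients (Statistical Plan).

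**Assumed inputs**
- Arterial SBP varies around its mean over a cuff cycle with SD *s* = 3 to 6 mm Hg.
- The recorder sees *k* = 3 to 8 independent values.
- The −24 (SD 17) is the difference from the mean arterial value.

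**Model.** Let D ~ N(−24, 17) be cuff minus mean arterial SBP, and let A₁…A_k ~ N(0, *s*) be the displayed deviations. The recorded difference is D minus the chosen A.

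1. *One value taken without selection.* The mean stays at −24 and the SD is √(17² + s²): √298 = 17.3, √305 = 17.5 and √325 = 18.0 for s = 3, 4 and 6.
2. *Value nearest the cuff, at every reading* (200,000 simulated pairs per setting).
3. *Nearest value at a fraction p of readings, otherwise unselected.* The shift is p times that in step 2.
4. *Highest value, at every reading.* The shift is −s × E[maximum of k standard normals]: 3 × 0.846 = 2.5; 4 × 1.163 = 4.7; 6 × 1.424 = 8.5. Simulating this rule gave means of −26.6, −28.6 and −32.6, within 0.1 of the exact values.

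| s, k | Nearest, always: mean (SD) | Shift toward agreement | Shift at p = 10% | Shift at p = 25% | Highest, always: mean |
|---|---|---|---|---|---|
| 3, 3 | −21.9 (16.4) | 2.1 | 0.2 | 0.5 | −26.5 |
| 4, 5 | −20.1 (15.9) | 3.9 | 0.4 | 1.0 | −28.7 |
| 6, 8 | −17.0 (15.0) | 7.0 | 0.7 | 1.7 | −32.5 |

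The last p = 25% entry is 0.25 × 6.97 = 1.74.

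**A different model.** Suppose the reference is pulled a fraction *w* of the way to the cuff. The shift is 24*w*: 1.2 mm Hg at w = 5% and 7.2 at w = 30%. The SD falls to 17(1 − *w*), that is 16.1 and 11.9. The range is similar, and *w* is again assumed.

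**Scale.** The margin is 10 mm Hg. With one difference per patient and n = 25, the 95% interval for the mean difference has half-width 2.064 × 17/√25 = 7.0 mm Hg. Selection at every reading would be comparable to these figures; occasional selection would be small beside them.

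**Between cuffs.** A false difference between two cuffs equals the difference between their shifts. It reaches 2.1 to 7.0 mm Hg only if nearest-value selection happens at every reading for one cuff and never for the other.

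**The case against.** The case on the other side is substantial.

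- *The mechanism is not described.* A reader might infer that someone copies the arterial value by hand from a moving display with the cuff result in view. The documents do not say so. Charting may mean automatic capture by the monitor or the electronic record, and charting at the same time argues against waiting for the cuff result and then choosing. This stands: the omission is established, a faulty procedure is not.
- *The direction is open.* A reader might infer false agreement. Background and Significance, however, hypothesises that cuffs under-read in these patients. A recorder led by that hypothesis would favour high arterial values and exaggerate the disagreement. This stands.
- *The larger shifts need extreme behaviour.* With a gap of 24 mm Hg, always taking the nearest value means taking the lowest displayed value in about 84–91% of readings. That is systematic selection rather than an inadvertent pull. This stands, and is why the 10% and 25% cases are shown.
- *Favouring the conical cuff.* A reader might take the phrase "A Breakthrough Solution for Accurate Bariatric Blood Pressure Readings" as a sign of allegiance. It is quoted advertising, followed by the intention to test the cuff, and is no evidence that the investigators favour it.
- *Cuffs cannot be masked.* This is inherent in comparing cuffs of different shape or site and is not a fault of the plan. It matters only because the reference, which could be protected, is not.
- *Scope.* The secondary comparison of cylindrical and radial cuffs with the conical cuff uses no arterial value and is untouched.

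None of this supplies the missing source, window or masking. If capture is already automatic, one sentence saying so would settle the source.

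**Conclusion.** The concern holds as a gap in specification. The arterial reference, on which every primary difference depends, has no stated source, no beat or averaging window, and no masking, and random cuff order does not fill the gap. Bias in cuff–arterial agreement is possible in either direction and could differ between cuffs.

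Neither its sign nor its size follows from the documents. Under the assumed SD of 3–6 mm Hg and 3–8 displayed values, the mean moves about 2–7 mm Hg toward agreement if the nearest value is taken every time, about 0.2–1.7 if this happens at 10–25% of readings, and about 2.5–8.5 away from agreement if the highest is always taken. These are illustrations, not estimates for this trial. The documents do not show that such bias will occur or that it would favour any cuff. The point is a cheap improvement and does not affect the sample size.

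**What to change.** Add to Methods:

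1. Arterial SBP, MAP and DAP are taken from the monitor's time-stamped stored numerics.
2. They are averaged over one window, fixed in advance relative to the cuff cycle and identical for every cuff.
3. The window lies outside cuff inflation, so that the same rule works when the cuff is on the catheter arm.
4. The values are extracted by time stamp, without sight of the cuff result.

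If stored numerics are unavailable, record the arterial value before the cuff result appears.

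The cost is a short protocol addition and a data-extraction step, with no extra procedure for the patient and no change in the number of patients. There are two drawbacks. Monitor and chart clocks must be matched. A window outside inflation is also not strictly simultaneous with the cuff reading, so it should lie close to it.

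### Charting arterial pressure simultaneously with each cuff reading allows the reference to be taken below an inflated cuff in up to 3 of 6 pairs per set, because neither the line arm nor the timing relative to inflation is specified

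*Combined protocol and SAP*

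**What the plan says.** In Methods of the combined protocol and SAP, systolic, mean and diastolic pressure are read from each of three cuffs: a large cylindrical upper arm cuff, a radial cuff and a conical cuff, which the title describes as an upper arm cuff. The readings are then "repeated after swapping the cuffs over to the opposite arm". They are sequential and in random order. On the device: "The BP cuffs will be linked to an Oscillometric BP recording device (Philips M1574A)". On the reference: "Direct invasive arterial pressure readings will be charted simultaneously for comparative purposes".

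Eligible women have a radial line already in place or are women "who agree to placement of an arterial line". The word radial is attached only to the lines already in place. The numbered list of items recorded for each arm covers two circumferences, upper arm length and cuff size. It does not include the arm that holds the line.

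The primary outcome is agreement of cuff systolic pressure with arterial systolic pressure. The Statistical Plan says: "Bland-Altman plots will be used to look at agreement of NIBP (SBP, MAP and DAP) and IBP". It has no stratum, exclusion or other rule for pairs in which the cuff and the line share an arm.

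**The concern.** An oscillometric reading requires the cuff to inflate. An inflated upper arm cuff lies upstream of a radial catheter in the same arm, and a radial cuff lies at or near it. While the cuff is inflated, the arterial trace is lost or reads low. This is a physical inference from the device and sites named in Methods; the documents do not discuss it.

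Because of the arm swap, every cuff is planned for the line arm once per set, so the conflict is built into the design. The plan does not say whether arterial pressure is charted before, during or after inflation.

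The reference for the primary outcome is at stake. If a falsely low arterial value is charted and analysed, the cuff appears to read higher than it does. Background and Significance hypothesises that cuffs under-read in these women, so the error would work against detecting what the trial looks for. The planned analyses relating arm taper (proximal minus distal circumference) to the cuff-arterial systolic difference use the same pairs. Comparisons of one cuff with another do not use the arterial value and are not affected.

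**Working it through.** **Inputs**
- 3 cuffs, each read on both arms (Methods).
- 25 women (Methods and Statistical Plan).
- Cuff minus arterial systolic difference of -24, SD 17 mm Hg, for oscillometric readings in the cited pre-eclampsia study of 23 women with BMI 19 to 45 (Background and Significance).
- From the Statistical Plan: "A difference of 10 mm Hg (SBP, MAP and DAP) will be considered clinically significant".
- Assumed: one line per woman, sited at the radial artery.

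The plan gives no number of pairs, so there is no stated figure to reproduce. The argument does not depend on how 25 was chosen.

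**Step 1: pairs exposed**
- Pairs per set: 3 cuffs x 2 arms = 6.
- On the line arm: 3 of 6 = 50%.
- First sets only: 25 x 6 = 150 pairs, of which 25 x 3 = 75 are on the line arm.
- If only the two upper arm cuffs compromise the line: 2 of 6 (33%).
- If the radial cuff cannot be placed on the line arm, 5 pairs remain and 2 of 5 (40%) are exposed.

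Exposed means that the cuff and line share an arm. It does not mean that the reference is wrong.

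**Step 2: what the timing decides**
- Arterial pressure read before inflation, or after the trace has recovered: no effect.
- Read during same-arm inflation: lost or falsely low.

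The wording permits either. The number of pairs actually affected therefore cannot be derived.

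**Step 3: direction and a hypothetical size**

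Let a share f of pairs have an arterial value that is too low by a fixed d mm Hg, unrelated to the true difference. Then:
- bias = -24 + f x d
- SD = sqrt(17² + f(1 - f)d²)
- half-width of the limits of agreement = 1.96 x SD

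With no affected pairs, the half-width is 1.96 x 17 = 33.3. With f = 0.5 and d = 20, the bias is -24 + 10 = -14, the SD is sqrt(289 + 0.25 x 400) = sqrt(389) = 19.7, and the half-width is 38.7.

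The fall d is assumed, so a range is shown:

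| f | d (mm Hg) | Bias | SD |
|---|---|---|---|
| 0 | 0 | -24.0 | 17.0 |
| 3/6 | 5 | -21.5 | 17.2 |
| 3/6 | 10 | -19.0 | 17.7 |
| 3/6 | 20 | -14.0 | 19.7 |
| 3/6 | 40 | -4.0 | 26.2 |
| 2/6 | 20 | -17.3 | 19.4 |
| 2/5 | 20 | -16.0 | 19.6 |

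The direction is fixed: any fall in the reference moves the bias upward. The size depends entirely on f and d, which the documents do not give. Repeat sets and correlation within a woman are not modelled.

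**The case against.** The strongest reply is that the harm rests on one reading of one word. Charted simultaneously may mean only that the arterial value is entered alongside the cuff value, and experienced staff would not record a trace that their own cuff has flattened. This stands as a reason not to claim an actual error. It does not close the gap: operators can resolve an unwritten rule differently, and the planned analysis has no means of showing that they did.

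Some stronger readings are tempting but not supported:

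- *Half the reference data are invalid.* Only exposure follows from the design. Each cuff also keeps one opposite-arm pair per set.
- *The conclusion would be reversed.* The 20 mm Hg case was picked for illustration. It shifts the bias by the plan's own 10 mm Hg, but the result of -14 still shows under-reading by more than 10. The starting values come from women with BMI 19 to 45, not from the trial population.
- *Affected pairs could never be found.* The list in Methods is not presented as a complete data form, the line side may be in the clinical chart, and a very large fall would be an obvious artefact. Moderate falls are harder to spot, and the side alone does not show when the value was read.
- *The lateral tilt makes a one-arm analysis biased by a known amount.* The sentence "The following measurements (left and right arm) will be made and recorded with the patient lying in a 15° left lateral tilt position" introduces the arm measurements; no position is stated for the pressure readings. Any height offset would become a group bias only if lines were mostly on one side, which the plan does not say. No figure is claimed for it.

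**Conclusion.** The point holds in a conditional form. Assuming one radial line per woman, up to 3 of 6 pairs per set, and up to 75 of 150 in the first sets, have the cuff on the line arm. The count is 2 of 6 or 2 of 5 under the alternatives for the radial cuff. If the charting sentence is followed literally, the primary-outcome reference in those pairs is lost or falsely low; if it is read outside inflation, it is sound. The plan does not say which applies, does not list the line arm among its measurements, and has no analysis rule for these pairs, so affected pairs may be hard to identify.

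The error, if it occurs, runs against the trial's hypothesis and widens the limits of agreement. Its size is unknown, and the figures above are illustrations. This should be fixed before data are collected, because timing cannot be restored afterwards. Confidence is medium: the exposure is clear given one radial line, the realised harm is not.

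**What to change.** In Methods, replace the charting sentence with:

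*The arm holding the arterial line (left or right) is recorded. For every cuff reading, on either arm, IBP is charted immediately before that cuff is inflated, from a stable arterial trace, and never during inflation of a cuff on the line arm.*

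The same timing on both arms matters: with different timing, arm and timing would be confounded.

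In the Statistical Plan, add:

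*Bias and limits of agreement for NIBP-IBP are reported for both arms together and separately for line-arm and opposite-arm pairs, with an opposite-arm-only sensitivity analysis. Pairs whose IBP was taken during same-arm inflation or was unreadable are excluded and counted by cuff and arm.*

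The cost is one data field and a few sentences. The number of women does not change. The arterial value precedes the cuff reading by seconds instead of coinciding with it. There may be a short pause for the trace to recover between line-arm readings. Since the plan has "There will be an initial set of readings on admission, and subsequent sets of readings before a medication administration", the pause lengthens each set by an amount the documents do not give. The opposite-arm-only analysis uses half the planned pairs, one per cuff per set, and so suits a sensitivity analysis better than the main one.

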Title: Non-invasive versus invasive blood pressure measurement in the morbidly obese parturient (BMI \geq 40 kg/m²) with severe preeclampsia: A comparison of direct arterial blood pressure measurements with readings obtained using either large cylindrical, radial cylindrical, or novel conical bariatric upper arm blood pressure cuffs.

Co-Investigators: [name]; [name] Sub-Investigators: [name]; [name]

; [name]; [name], [name], [name], MD, [name]

Vanderbilt University Medical Center

OB Anesthesiology

Aim: To compare agreement of invasive blood pressure measurements with non-invasive blood pressure measurements measured with a conical blood pressure, radial cuff, and large standard upper arm rectangular cuff in morbidly obese severely hypertensive (systolic blood pressure > 160 mmHg) parturients.

Background and Significance: A morbidly obese [Body Mass Index (BMI) \geq 40 kg/m²] pregnant woman is at singular risk for all the complications of pregnancy, most notably preeclampsia (PE) ^{1, 2}. Furthermore a woman who is already chronically hypertensive is quite likely to develop superimposed PE ^{3,4}. Uncontrolled systolic hypertension in pregnancy prompts placental abruption, hemorrhagic stroke, and systolic or diastolic heart failure. Mhyre rightly asserts that: "Systolic blood pressure ... above 160 mm Hg constitutes a hypertensive crisis in a pregnant woman and requires urgent treatment to minimize risk for cerebral hemorrhage" ⁵. The American College of Obstetrics and Gynecology Task Force on Hypertension in Pregnancy also now recommends the use of antihypertensive therapy for persistent severe maternal hypertension (SBP at or above 160 mm Hg) ⁶. Accurate blood pressure measurement is therefore a prerequisite to controlling dangerously high SBP to enable labor and delivery to be conducted safely in association with PE. An algorithm has been implanted on Vanderbilt Labor and Delivery, using SMFM guidelines, to guide treatment of these severe range blood pressures²⁰. Precise SBP measurement is also a precondition for clinically testing hypotheses concerning the existence of druggable targets that will allow prolongation of pregnancy in the face of severe PE and /or intra-uterine growth restriction (IUGR) remote from term ^{7,8}.

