Hypertensive hemorrhagic stroke is the most common cause of maternal death related to preeclampsia 5 . Upper arm SBPs measured with a standard rectangular cylindrical cuff exceeding 160 mm Hg are not infrequently seen in severe preeclampsia. During general anesthesia for cesarean section direct arterial SBPs well in excess of 160 mm Hg have been recorded during both laryngeal intubation and extubation 9,10 . SBPs this high place the preeclamptic parturient at serious risk for hemorrhagic stroke 5 . We hypothesize that measurement of noninvasive blood pressure (NIBP) in morbidly obese patients (BMI \geq 40) with large upper arm circumferences

adds a further margin of under-reading error when compared with direct arterial, invasive blood pressure (IBP) recording, thus compounding the risk of maternal stroke.

Oscillometric NIBP measurement is the customary standard blood pressure monitoring method most often used in the labor suite and obstetric operating room today. For this purpose a rectangular, cylindrical blood pressure (BP) cuff placed on the upper arm is connected to an oscillometric blood pressure device. Yet inaccuracies related to the fact that oscillometric NIBP devices under-read high SBP relative to IBP measurements have been recognized as a potential source of maternal morbidity for years ¹¹. A decade ago Martin et al. highlighted the importance of treating SBP rather than diastolic blood pressure (DAP) to avoid stroke in severe preeclampsia and eclampsia, concluding that: "A paradigm shift is needed toward considering antihypertensive therapy for severely preeclamptic and eclamptic patients when systolic blood pressure reaches or exceeds 150-160 mm Hg." ¹².

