In non-pregnant patients a recent retrospective analysis of data obtained from a cohort of more than 15,000 men and women showed that systolic, mean, and diastolic upper arm blood pressures measured non-invasively with rectangular, cylindrical blood pressure cuffs that fell within the normal range correlated relatively well with direct IBP recordings obtained via a radial artery catheter, the latter method currently representing the "gold standard" for clinical BP determination ¹³. However, outside the normal ranges NIBP tended to under read at higher pressures but paradoxically, over read at lower blood pressures. Cross over points for SBP, MAP and DAP agreement between NIBP and IBP were noted to be 111, 95 and 80 mm Hg respectively. Similar disparities between NIBP and IBP recordings in hyperacute stroke patients have been documented ¹⁴. A recent systematic review of the subject under scrutiny here confirms the relative inaccuracy of current NIBP methods when compared to IBP recording ¹⁵.

Rectangular, cylindrical BP cuffs have been noted to overestimate SBP relative to tronchoconical cuffs in morbidly obese (mean body mass index $41.4 \pm \text{SEM } 0.7$) men and women (group 4) by as much as 9.7 mm Hg , most notably in those subjects with shorter upper arm lengths 16 . The incidence of hypertension among this group of morbidly obese patients was purported to be 54.6% using the cylindrical cuff, but was found to be only 40.0% using the conical cuff (p < 0.001). Thus 15% of subjects who appeared hypertensive with the cylindrical cuff were actually normotensive. In contrast, in a limited study of "severely" obese male and female subjects (n = 16) NIBPs measured on the upper arm with both cylindrical and conical cuffs, and on the forearm with cylindrical cuffs were noted to be little different from corresponding radial artery catheter pressures 17 .

With regard to pregnancy, Langenegger et al. compared both manual ausculatory and automated oscillometric NIBP to direct arterial IBP when monitoring acute severe hypertension in 23 preeclamptic patients (gestational ages 22 - 40 weeks; BMI 19 - 45) 18 . Mean oscillometric SBP (148 \pm 18 mm Hg) and manual auscultatory readings (152 \pm 15) were on average 24 \pm 17 and 20 \pm 15 mm Hg respectively lower than the direct arterial SBP recordings (172 \pm 11 mm Hg). To

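### No planned estimate compares the three cuffs' errors against arterial pressure within the same woman; the explicit cuff-to-cuff analyses use the conical cuff as comparator

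*Combined protocol and SAP*

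**What the plan says.** The Aim is "To compare agreement of invasive blood pressure measurements with non-invasive blood pressure measurements measured with a conical blood pressure, radial cuff, and large standard" upper-arm cuffs. The primary outcome is to "compare the agreement of NIBP and SBP measurements relative to IBP SBP recordings". The Background calls the radial artery catheter the reference standard, and the Methods chart arterial pressure simultaneously with the cuff readings, which are taken in sequence and in random order.

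The outcome paragraphs and the Statistical Plan contain four kinds of analysis:

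- **Bland-Altman against arterial pressure:** "Bland-Altman plots will be used to look at agreement of NIBP (SBP, MAP and DAP) and IBP". The sentence does not say one plot per cuff.
- **Arm taper against error:** the difference between proximal and distal arm circumference is related to cylindrical-minus-arterial systolic pressure and, separately, to conical-minus-arterial. The two relations are not compared, and the radial cuff is left out.
- **Cuff-to-cuff agreement:** a secondary outcome is "to compare agreement of the SBP, MAP and DAP NIBP measurements obtained with cylindrical upper arm and radial BP cuffs with those recorded using conical" cuffs.
- **Circumference regression in the Statistical Plan:** the outcome is cylindrical or radial against conical.

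A difference of 10 mm Hg is called clinically significant, without saying which comparison it applies to.

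**The concern.** The comparison that the Aim implies is between errors: is one cuff's reading closer to the artery than another's in the same woman? The ingredients are collected, but no planned estimate or interval puts them together. The explicit cuff-to-cuff items use the conical cuff as comparator, so they measure whether two cuffs can be exchanged, not which one is accurate.

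The direction matters here. The protocol hypothesises that cuff measurement in large arms "adds a further margin of under-reading error when compared with direct arterial, invasive blood pressure (IBP) recording". The Background also reports that "Rectangular, cylindrical BP cuffs have been noted to overestimate SBP relative to tronchoconical cuffs in morbidly obese" subjects. If cuffs under-read in this population, a cylindrical cuff that reads higher than the conical one may be the nearer of the two, although a conical-referenced analysis shows it as reading high. Without a planned contrast against arterial pressure, the reader must rank the cuffs by eye from separate plots.

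**Working it through.** **Inputs from the Background and Methods**

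- Oscillometric systolic pressure against arterial, in the cited preeclampsia study: 148 - 172 = -24 mm Hg, which matches the stated 24. The SD of the difference is 17.
- Cylindrical minus conical, in the cited study of morbidly obese adults: up to +9.7 mm Hg.
- 25 women; criterion 10 mm Hg.

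**Assumptions not in the documents:** one averaged error per cuff per woman, normal errors with SD 17 for every cuff, and correlation ρ between two cuffs' errors within a woman.

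**Step 1. What a cuff-to-cuff difference identifies.** Let b be a cuff's mean error against arterial pressure. Without drift, cylindrical minus conical estimates b_cyl - b_con. Three pairs give the same +9.7. For the mean absolute error, E|X| = σ√(2/π)·exp(-b²/2σ²) + b·[1 - 2Φ(-b/σ)] with σ = 17:

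| b_cyl, b_con | Difference | Mean absolute error, cyl / con | Nearer the artery |
|---|---|---|---|
| +9.7, 0 | +9.7 | 15.7 / 13.6 | conical |
| +4.85, -4.85 | +9.7 | 14.1 / 14.1 | tie |
| -24, -33.7 | +9.7 | 25.2 / 34.0 | cylindrical |

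With the difference fixed at +9.7, the conical cuff has the smaller bias only if b_cyl > 9.7/2 = 4.85.

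**Step 2. The cuff-to-cuff test alone.** In 20,000 simulated trials of 25 women, the paired t-test of cylindrical against conical is significant in about 78%, 94% and 99% of trials at ρ = 0.5, 0.7 and 0.8. The rates are the same in all three rows, so this test alone cannot separate them.

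**Step 3. Drift.** With sequential readings,

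raw difference = (error_cyl - error_con) + (arterial at cylindrical reading - arterial at conical reading).

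The second bracket is true pressure change. Random order should keep it from favouring one cuff on average, but it still adds scatter. Subtracting each cuff's own simultaneous arterial value removes it.

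**Step 4. Precision of the missing contrast.** SD of the paired difference in signed error = 17√(2(1 - ρ)); 95% half-width = 2.064 × SD/√25.

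| ρ | SD | Half-width, mm Hg | Power for 10 mm Hg, two-sided 5% |
|---|---|---|---|
| 0 | 24.0 | 9.9 | 51% |
| 0.25 | 20.8 | 8.6 | 64% |
| 0.5 | 17.0 | 7.0 | 81% |
| 0.75 | 12.0 | 5.0 | 98% |

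A single cuff's bias has half-width 2.064 × 17/5 = 7.0. A single limit of agreement has 2.064 × 17 × √(1/25 + 1.96²/48) = 12.2.

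**Step 5. Signed or absolute error as the main contrast.** In the third row of Step 1, two results together (both bias intervals below zero, and a significant signed difference) identify the nearer cuff in 78%, 94% and 99% of trials at ρ = 0.5, 0.7 and 0.8. A paired test of absolute error does so in 74%, 91% and 98%. In the first row, and at biases of (0, -9.7), the absolute-error test has only about 11 to 15% power.

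**The case against.** The strongest reply is that arterial pressure already is the plan's main reference. The Aim, the primary outcome and the first secondary outcome all use it, the taper relations use each cuff's error against it, and conical-referenced agreement is a later secondary outcome. All of that stands. A reader might infer that the plan uses the wrong yardstick throughout, or will choose the most accurate cuff by its agreement with the conical one. The documents do not say so. The Background does describe some subjects as truly normotensive on the strength of the conical reading, but this summarises one cited study. The following sentence reports a study of 16 severely obese subjects in which both cuff shapes differed little from arterial pressure.

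A second reply is that separate Bland-Altman results, read beside the cuff-to-cuff difference, can identify the nearer cuff. Step 5 confirms this for the large-bias case, provided that the plots are per cuff, carry intervals, and drift is negligible. The plan states none of these.

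A reader might also infer that the cuffs will be judged by whether their separate confidence intervals overlap. No such rule is in the plan, so it should not be criticised on that ground.

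Finally, the illustrative inputs are stretched. The 9.7 is a maximum in men and women not described as pregnant. The -24 comes from women with BMI 19 to 45, and the cuff shape is not given. The argument in Step 1 does not depend on either value.

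**Conclusion.** The concern holds as a gap in the Statistical Plan. The Aim concerns three cuffs' agreement with arterial pressure, yet no planned estimate or interval compares their errors against it within the same woman, and the explicit cuff-to-cuff items use a comparator that cannot show accuracy. A difference of +9.7 mm Hg is compatible with either cuff being nearer, or with a tie.

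The planned readings should support the missing contrast. With 25 women and an error SD of 17, its 95% half-width runs from 9.9 mm Hg at ρ = 0 to 5.0 at ρ = 0.75, so it is informative against 10 mm Hg unless the correlation is low. These figures rest on equal SDs, one averaged value per cuff per woman and an assumed ρ.

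That a cuff-to-cuff difference could mislead about accuracy is a possibility shown with illustrative values, not a prediction for this trial. The plan should be changed before analysis; the data collection is not affected.

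**What to change.** In the Statistical Plan:

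1. Report Bland-Altman bias and limits of agreement against simultaneous arterial pressure separately for the conical, upper-arm cylindrical and radial cuffs, each with a 95% CI.
2. Add the within-woman paired difference between cuffs in signed systolic error (cuff minus simultaneous arterial), with a 95% CI from a mixed model with woman as a random effect or a cluster bootstrap by woman. Terms for arm, order and reading set suit the design. Read the difference beside each cuff's own bias, since its sign alone does not say which cuff is nearer, and against the 10 mm Hg criterion.
3. Report the paired difference in absolute error as supportive.
4. Keep conical-referenced agreement, labelled as interchangeability and not accuracy.

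The cost is wording and modest analysis work, with no new patients or readings. The downsides are small: there are more contrasts to report, and absolute error has low power when the biases are small. If all three cuff pairs are tested with a Bonferroni level of 0.0167, power at 25 women for 10 mm Hg falls from 81% to 65% at ρ = 0.5, so the plan should say which contrast leads.
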